4. STATISTICAL CONSIDERATIONS

4.1 Sample Size and Power

The primary analysis will be based on HIV incidence during Steps 1 and 2. As described previously, we assume that participants will be followed between 81 (latest enrollees) and 185 (earliest enrollees) weeks in Steps 1 and 2 (1.6 – 3.6 years), with a uniform distribution of enrollments over a two-year period. Thus, average time in Steps 1 and 2 will be 133 weeks (2.6 years). Sample size calculations are based on the following assumptions:

- Background HIV incidence, in the absence of any PrEP, is 3.5% per year
- Both CAB LA and TDF/FTC are 85% effective when used with 100% adherence
- 2.5% one-sided type I error rate and 90% power at the indicated alternative
- Average follow-up duration of 2.6 years (range: 1.6 – 3.6 years)
- Maximum 5% lost-to-follow-up per year

Table 4.1 presents five scenarios and associated total sample sizes. All are superiority designs. The first scenario assumes that adherence to TDF/FTC and CAB/CAB LA will be 50% and 85%, respectively, averaged over the entire Step 1 and 2 follow-up period. The second and third scenarios assume a higher adherence to TDF/FTC (second line) and lower adherence to CAB LA (80%) (third line) (these scenarios are considered unlikely). The last two scenarios retain the conservative assumption of 80% adherence to CAB LA and assume lower adherence to TDF/FTC of 45% and 48%. The largest blinded trials of TDF/FTC among women in a similar setting have shown even lower adherence than assumed in Table 4.1.

Given this history we believe that a sample size of at least 3,128 (111 events for a fixed sample size trial; we will target 114 events to allow for interim monitoring) provides an adequate degree of robustness against uncertainties in adherence rates to the two drug regimens. The trial will continue until we reach 114 events, or a stopping boundary is crossed (see below).

Table 4.1. Five Case Scenarios

Adherence		HIV Incidence (%/year) ¹				
TDF/FTC	CAB LA	TDF/FTC	CAB LA	RR	Number Events	Sample Size
.50	.85	2.01	0.97	.48	78	2352
.55	.85	1.86	0.97	.52	98	3112
.50	.80	2.01	1.12	.56	125	3590
.48	.80	2.07	1.12	.54	111	3128
.45	.80	2.16	1.12	.52	98	2686

¹Background incidence is reduced by a weighted average of fully adherent and non-adherent individuals e.g. 2.01 = $3.5 * ((1 - .85) * .5 + 1 * (1 - .5))$

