4.2 Randomization

Participants will be randomized to one of two study arms in a 1:1 ratio. Randomization will be stratified by study site, and a permuted blocks design will be used to ensure balanced treatment assignments within study site. The randomization scheme will be generated, operationalized and maintained by the HPTN Statistics and Data Management Center.

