7.3.2. Primary Safety Analysis

Objective: To evaluate the relative safety of oral CAB/CAB LA (oral run-in and injections, Steps 1 and 2) vs. daily oral TDF/FTC for HIV prevention (Steps 1 and 2).

Population: Safety population

The primary pre-specified safety comparison between arms will be based on all AEs with maximum grade ≥ 2 . In general, formal statistical comparison of individual types of safety events across arms is not planned since interpretation of differences must rely heavily upon clinical judgment. Where formal statistical testing is considered necessary to guide judgement of observed differences for any single event or collection of events, differences in events grade 2 and higher will be assessed. The event rate and 95% robust confidence interval for each treatment arm will be calculated using a log-linear model for counts using log(person-time) as an offset, treatment as a covariate, assuming a Poisson distribution and using a robust variance (i.e. generalized estimating equations). Event rates will be compared between treatment arms using this same model. Event rates will be compared between treatment arms using this same model and a type I error rate of $\alpha=0.05$ is prespecified. Very rare events will be compared using an exact Poisson test. Additional supporting descriptive safety analyses will be presented.

For Safety OBSP analysis, adverse event follow-up will be censored after the last injection before a termination or a permanent product discontinuation regardless of any delays in injections. If termination or a permanent product discontinuation occurs prior to their first injection, the participant's follow-up time will be censored at the termination or permanent product discontinuation date +1. If termination or a permanent product discontinuation occurs after the first injection, the participants follow-up time will be censored up through 6 weeks after the Week 5 injection, if that is the last injection, or 10 weeks after the last injection for subsequent injections.

7.3.3. Adverse events in Step 1

Objective: To compare the safety of oral CAB vs. oral TDF/FTC in Step 1

Population: Primary Safety

Censoring: AEs are censored at 120 days after randomization for participants who never received an injection; at 1 day after the date of termination or investigational product discontinuation; at date of first injection, whichever occurs first. Reported AEs will be excluded if they occur after the censoring time.

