A set of tables will describe retention in follow-up for participants at each scheduled study visit. Number of women enrolled, number of women expected at each visit, number of women attending the visit early, late and on time, and percent retained will be presented. A separate retention report will be generated for women who have moved to alternative visit schedules (e.g. pregnancy, open-label TDF/FTC, annual testing); these women's visits will not be included in the standard retention table after they move to an alternative visit schedule. Retention will be presented overall and by site in the open report and by study arm in the closed report. No formal statistical testing will be performed.

- **Fidelity of Intervention**

A set of tables will describe the proportion of injections provided and the proportion of pill bottles distributed at each visit, among those retained at the visit. These tables will be presented overall and by site in the open report and by study arm in the closed report. No formal statistical testing will be performed.

- **Safety Reports (Closed Reports)**

The number and percentage of participants experiencing local reactions to the injections will be tabulated by severity and treatment arm. For a given local reaction type, each participant's

reaction will be counted once under the maximum severity for all injection visits. In addition to the individual reaction types, the maximum severity of local pain or tenderness, induration or erythema, and of systemic symptoms will be calculated. AEs will be summarized using MedDRA System Organ Class and preferred terms. Tables will show by treatment arm the number and percentage of participants experiencing an AE within a System Organ Class or within preferred term category by severity. For the calculations in these tables, a participant with multiple AEs within a category will be counted once under the maximum severity.

A listing of SAEs reported to the DAIDS Regulatory Support Center (RSC) Safety Office will provide details of the events including severity, time between onset and last dosing, and cumulative number of doses received.

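### The exact Poisson test for very rare adverse events drops the within-woman allowance of the main safety model and names no participant-level unit, so its type I error is not held at .05 if women have repeat events

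*SAP*

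**What the plan says.** SAP section 7.3.2 defines the main comparison in terms of events: "The primary pre-specified safety comparison between arms will be based on all AEs with maximum grade" 2 or higher. Rates come from a log-linear model for counts with person-time as offset, "assuming a Poisson distribution and using a robust variance (i.e. generalized estimating equations"). The level is set in the sentence "Event rates will be compared between treatment arms using this same model and a type I error rate of" 0.05. The next sentence gives the fallback in full: "Very rare events will be compared using an exact Poisson test". It gives no unit (events or women), no threshold for very rare and no rule for repeats.

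Sections 7.3.3 (Step 1) and 7.3.4 (Step 2, on blinded study product) refer back to the same analysis.

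A once-per-woman rule does appear, but for tables. Section 9.1 says "a participant with multiple AEs within a category will be counted once under the maximum severity", and section 7.3.7 b uses the same rule for its tables by system organ class. Section 9.2 assigns the greatest severity per preferred term in summaries.

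Section 7.3.2 also limits the role of such tests: "formal statistical comparison of individual types of safety events across arms is not planned since interpretation of differences must rely heavily upon clinical judgment".

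**The concern.** Women are randomised, but the outcome is a count, so one woman can contribute several events. The main model handles this through its robust variance. The exact Poisson test conditions on the total number of events and treats each as an independent draw between arms. If the count outcome carries over from the same paragraph, which is the natural reading, the protection is lost where events are few and one woman has most leverage.

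The missing unit matters even without a simulation. Suppose three women in one arm have two events each and the other arm has none. Counting events gives p = 2 × (1/2)^6 = .031. Counting women gives p = 2 × (1/2)^3 = .25. The same data support either result, and nothing in the SAP fixes the choice before the data are seen.

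The SAP is more careful elsewhere. Section 7.3.1 confirms the HIV result by permuting treatment assignments when there are fewer than 40 events. Section 7.3.7 f turns to a permutation test when women have several observations.

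**Working it through.** **Inputs from the SAP.** Nominal level 0.05 (7.3.2). Allocation: "Participants will be randomized to one of two study arms in a 1:1 ratio" (4.2). Time in which an event could recur: "average time in Steps 1 and 2 will be 133 weeks (2.6 years") (4.1).

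**Assumptions.** Equal person-time in the two arms, no true arm difference, and a range of recurrence rates, because the SAP gives none.

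**Test.** With *n* events in total and *x* in one arm, the two-sided exact test refers *x* to Binomial(*n*, 1/2). Its true size is found by letting each affected woman, with all her events, fall in either arm with probability 1/2.

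**1. No repeats (the plan's own level).** For *n* = 12 the test rejects at *x* ≤ 2 or *x* ≥ 10. Size = 2 × (1 + 12 + 66)/4096 = 158/4096 = .039. The stated .05 is respected, with slack from discreteness.

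**2. Five or fewer events.** The most extreme split, 5 to 0, gives p = 2 × (1/2)^5 = .0625. The test cannot reject, whatever the clustering.

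**3. One woman with four events, plus eight single events (*n* = 12).** Her arm has at least 4 events, so rejection needs that arm to reach 10, which means at least 6 of the 8 singles. Size = (28 + 8 + 1)/256 = 37/256 = .145.

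**4. Two women with two events each, plus eight singles (*n* = 12).** Both women fall in the same arm with probability 1/2, and rejection then has probability 37/256. They fall in different arms with probability 1/2, and rejection then needs all eight singles in one arm, 2/256. Size = (37 + 2)/512 = .076.

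**5. Other totals, by the same enumeration.**

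| Events in total | No repeats | 1 woman with 2 | 2 women with 2 | 3 women with 2 |
|---|---|---|---|---|
| 6 | .031 | .063 | .125 | .250 |
| 8 | .008 | .016 | .031 | .063 |
| 9 | .039 | .063 | .094 | .125 |
| 10 | .021 | .035 | .055 | .078 |
| 12 | .039 | .056 | .076 | .098 |
| 20 | .041 | .052 | .063 | .075 |
| 30 | .043 | .050 | .057 | .065 |

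Over every total from 6 to 30, one or two women with a single repeat give .016 to .078, except two such women at 6 events (.125) or 9 events (.094).

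**6. Random totals.** Affected women per arm are Poisson with mean 4, 6 or 10. Events per affected woman are geometric or 1 + Poisson. There are 40,000 replicates per cell.

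| Mean events per affected woman | Test on events | Test on women |
|---|---|---|
| 1 | .018–.030 | .018–.030 |
| 1.25 | .056–.076 | .018–.029 |
| 1.5 | .095–.128 | .017–.030 |
| 2 | .166–.219 | .017–.030 |

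**7. Permutation test on per-woman counts.** In the configuration of step 3 its size is .035, and in that of step 4 it is .018. Both are below .05 while repeats still count.

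**The case against.** The strongest reply is that the SAP never says the exact test uses repeat events. Section 7.3.2 speaks of maximum grade, and the tables collapse repeats under maximum severity. If each woman is counted once, the difficulty disappears. That stands as a possible reading, so it cannot be said that the SAP definitely counts repeats as independent. It is the less natural reading: the outcome and model in 7.3.2 are counts, and in 7.3.7 b the once-per-woman rule governs the tables while the rate again comes from a count model with robust variance.

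A reader might infer that a few recurrences push the error rate well above .05. The figures do not support that in general. Discreteness leaves slack, and rates of .10 or more mostly need about half the affected women to repeat or one woman to have several events. The values at 6 and 9 events are exceptions.

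A reader might also infer that exact confidence limits would be too narrow. The SAP specifies no exact interval; the only interval in 7.3.2 is the robust one.

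It is also fair that tests of individual event types are used only where needed to guide judgement, that by-subject listings would show one woman contributing several events, that section 7.2.4 sets no formal safety stopping rule, and that Step 1, at about five weeks, leaves little room for recurrence. These points lower the priority; they do not supply the missing unit.

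**Conclusion.** The point holds as a gap in specification with a conditional effect on type I error. If the exact Poisson test is run on event counts, its level is not guaranteed once women have repeat events. The excess is small or absent with one or two single repeats and becomes material at a mean of about 1.5 events per affected woman or when one woman recurs several times. All these sizes rest on assumed recurrence and equal person-time.

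It should not be read as a fault in the primary safety comparison. All adverse events of grade 2 or higher are not very rare, and that analysis keeps its robust variance. Priority is low to moderate.

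**What to change.** Replace the sentence in section 7.3.2 with wording such as: *Very rare events (fewer than [number] events across both arms) will be compared using a permutation test of treatment assignment, within site, applied to the event count of each participant with person-time taken into account.* This keeps the event rate as the target and follows the approach of sections 7.3.1 and 7.3.7 f. Permuting within site respects the stratified randomisation in section 4.2.

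The alternative is to keep the exact Poisson test but apply it to the number of participants with at least one event, with person-time censored at the first event. That changes the target to the incidence of a first event, and repeats do not add to the test; they remain in the listings.

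Either way, fill in the threshold for very rare before unblinded results are seen. Sections 7.3.3 and 7.3.4 then inherit the change. The cost is one sentence and a short program; no new data are needed.

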Descriptive and Statistical Analysis as above

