7.3.4. Adverse events Step 2 only OBSP

Objective: To compare the safety of CAB LA vs. oral TDF/FTC proximal to blinded study drug administration

Population: Step 2 safety

Censoring: AEs are censored using ON BLINDED STUDY PRODUCT (OBSP) censoring.

Details of the OBSP censoring definitions are given in Appendix B. Reported AEs will be excluded if they occur before the first injection or after the OBSP censoring time.

Descriptive and Statistical Analysis will be performed as above

7.3.5. *Laboratory evaluations*

Population: Primary Safety

Descriptive: Laboratory findings for CBC, chemistries (urea, creatinine, CPK, glucose, calcium, phosphorous, amylase, lipase), liver function (AST, ALT, total bilirubin, alkaline phosphatase) and fasting lipid profile (total cholesterol, triglycerides, HDL, LDL) will be reported by grade, as defined in the “Division of AIDS (DAIDS) Table for Grading the Severity of Adult and Pediatric Adverse Events”. The proportion of laboratory findings qualifying as Grade 2 or above will be presented. Laboratory values will be reported by arm as median, 1st and 3rd quartiles, min and max, and (at follow-up visits) as median, 1st and 3rd quartile change from baseline (see below). Summaries involving values and changes from baseline at scheduled visit time points will consider values from scheduled visits only, and in the case of missing values, results will not be carried forward from interim (unscheduled) visits. For summaries and analyses involving changes in laboratory values over time or maximum change from baseline (e.g. shift tables), values from interim (unscheduled) visits will also be considered.

Formal comparisons of laboratory values will be conducted as follows:

- Absolute values: A mixed-effects model with participant as the random effect and site and arm as fixed effects will be used to assess overall differences in each laboratory outcome by arm. Outcomes with highly skewed distributions will be log-transformed. A continuous time (elapsed study time) term and an interaction of time with study arm will be added to model time trends in laboratory values that may emerge with continuous exposure to study drug. Only post baseline visits will be included.

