8.2. Missing Start and Stop Dates for Adverse Events

The Assumption is to consider the most conservative judgment when imputing.

Start date:

1. If start date is completely missing, start date is set to date of first dose.
2. If (year is present, and month and day are missing) or (year and day are present, and month is missing):
 - a. If year = year of first dose, then set month and day to month and day of first dose.
 - b. If year < year of first dose, then set month and day to December 31st.
 - c. If year > year of first dose, then set month and day to January 1st.
3. If month and year are present and day is missing:
 - a. If year = year of first dose and
 1. If month = month of first dose, then set day to day of first dose date.
 2. If month < month of first dose, then set day to last day of month.
 3. If month > month of first dose, then set day to 1st day of month.
 - b. If year < year of first dose, then set day to last day of month.
 - c. If year > year of first dose, then set day to 1st day of month.

Stop date:

If the outcome of the AE was ongoing or unknown, then the rules outlined below will not be applied.

1. If stop date is completely missing, stop date is set to date of study discontinuation.
2. If (year is present, and month and day are missing) or (year and day are present, and month is missing):
 - a. If year = year of study discontinuation, then set month and day to month and day of study discontinuation.
 - b. If year < year of study discontinuation, then set month and day to December 31st.
 - c. If year > year of study discontinuation, then set month and day to December 31st.
3. If month and year are present and day is missing:
 - a. If year = year of study discontinuation and
 - i. If month = month of study discontinuation, then set day to day of study discontinuation date
 - ii. If month < month of study discontinuation, then set day to last day of month.
 - iii. If month > month of study discontinuation, then set day to last day of month.
 - b. If year < year of study discontinuation, then set day to last day of month.
 - c. If year > year of study discontinuation, then set day to last day of month.

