APPENDIX E – Adverse Events of Special Interest

Adverse events of special interest (AESI) have been determined for CAB based on pre-clinical and clinical experience, along with information for the integrase inhibitor class of HIV medications safety profile. These are adverse events for which more detailed summaries of event characteristics are of interest. Details of the analyses of AESI are contained in Section **Error! Reference source not found.** based on the current MedDRA version used for the study, v23.1.

The identification and classification of AESI will have occurred as a clinical review of preferred terms for adverse events, lab data, ECG and vital signs prior to the unblinding of the studies. (see Appendix E Section 1).

Table 1 shows the adverse events of special interest identified and reasons for including.

Table 1 Adverse Events of Special Interest

AESI	Product Implicated	Reason for Including as AESI
Hepatic Safety Profile: Assessment of risk of hepatotoxicity	CAB	Clinical, Class, Regulatory Interest,
Hypersensitivity Reactions (HSR)	CAB	Class, Regulatory Interest,
Rash	CAB	Class, Regulatory Interest
Neuropsychiatric Events 
 • Suicidal Ideation/Behaviour • Depression • Bipolar Disorder • Psychosis • Mood Disorders • Anxiety • Sleep Disorders 	CAB	Clinical, Class, Regulatory Interest,
Injection Site Reactions (ISR)	CAB	Clinical, Regulatory Interest
Seizures and Seizure-like events	CAB	Clinical, Regulatory Interest
Weight Gain	CAB	Clinical, Class, Regulatory Interest
Rhabdomyolysis	CAB	Clinical, Class, Regulatory Interest
Pancreatitis	CAB	Clinical, Therapeutic Area, Regulatory Interest

Impact on Creatinine	CAB	Regulatory Interest, Therapeutic Area
Safety in Pregnancy (Does not apply to HPTN083)	CAB	Regulatory Interest, Class
Hyperglycaemia/new onset diabetes mellitus	CAB	Observation from 083, Class

Common ISR adverse events are defined by MedDRA preferred terms including injection site pain, injection site induration, injection site nodules and preferred terms of any other ISR with $\geq 5\%$ participants in either treatment arm. ISRs are summarized and listed regardless of IP relationship.

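### The Step 1 and Step 2 adverse-event rules both keep events dated on the day of the first injection, so injection reactions can enter the oral run-in comparison

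*SAP*

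**What the plan says.** SAP Section 7.3.3 gives the objective of the Step 1 safety analysis as "To compare the safety of oral CAB vs. oral TDF/FTC in Step 1". Its censoring rule takes the earliest of several dates. For a woman who goes on to injections, the one that applies is "at date of first injection, whichever occurs first. Reported AEs will be excluded if they occur after the censoring time". The analysis itself is given only as "Descriptive and Statistical Analysis as above", which points back to Section 7.3.2. There, rates are "calculated using a log-linear model for counts using log(person-time) as an offset", and "The primary pre-specified safety comparison between arms will be based on all AEs with maximum grade" 2 or higher.

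Section 7.3.4 covers Step 2 on blinded study product. Its rule is "Reported AEs will be excluded if they occur before the first injection or after the OBSP censoring time".

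Three other places bear on the boundary. Appendix A lists the Week 5 visit, when injections start, as Day 0 of Step 2. Appendix E treats injection site reactions as adverse events: "Common ISR adverse events are defined by MedDRA preferred terms including injection site pain". It also says that they are reported whatever their relationship to product. Section 2.7.2 gives Arm B a matching vehicle injection of identical volume, so women in both arms are injected that day.

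**The concern.** The two rules do not divide the timeline cleanly. Step 1 drops an event only if it falls after the injection date, and Step 2 drops one only if it falls before the injection. An event on the date itself survives both. The SAP gives no tie rule, no clock-time rule and no exclusion of injection reactions from Step 1.

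Events on that day are likely to include reactions to the injection. These are not effects of five weeks of oral product, yet a programmer who follows the text exactly will count them in the oral run-in rate. That rate has a short denominator, so a small number of events can raise it visibly. If active and vehicle injections differ in same-day reactions, part of that difference would appear as a difference between oral CAB and oral TDF/FTC.

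**Working it through.** The SAP states no figure on this point, so there is none to reproduce. The check has three parts.

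**1. The two rules applied by calendar date**

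| AE onset relative to first injection | Step 1 (drop if after) | Step 2 (drop if before) |
|---|---|---|
| 1 day before | kept | dropped |
| same day | kept | kept |
| 1 day after | dropped | kept |

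Reading Step 2 by clock time does not remove the problem. Section 7.3.3 sets its boundary explicitly as a date, so a reaction after the injection on the same day still stays in Step 1.

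**2. Effect on one arm's Step 1 rate**

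Inputs from the SAP:
- Run-in of five weeks, or 35 days (Section 2.7.1).
- About 3,350 women randomized 1:1, or 1,675 per arm (Sections 4.2 and 4.4).
- Average time in Steps 1 and 2 of 133 weeks (Section 4.1), which leaves about 133 − 5 = 128 weeks for Step 2.

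Run-in person-time per arm is 1,675 × 35/365.25 = 160.5 person-years. If a share p of women has a counted event on the injection day, the added rate is p / (35/365.25). For p = 1% this is 0.01/0.0958 = 0.104 per person-year, or 10.4 per 100 person-years.

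| Assumed share with a grade 2 or higher AE that day | Added to Step 1 rate, per 100 person-years |
|---|---|
| 0.1% | 1.0 |
| 0.5% | 5.2 |
| 1% | 10.4 |
| 2% | 20.9 |
| 5% | 52.2 |

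Over Step 2 the same 1% adds only 0.01/(128 × 7/365.25) = 0.0041 per person-year, or about 0.4 per 100 person-years. The misplacement therefore matters in Step 1 and hardly at all in Step 2.

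The Step 1 figures are approximate upper values. Women who are never injected can contribute up to 120 days of Step 1 time under Section 7.3.3 and no injection-day events.

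**3. Effect on the ratio between arms**

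With a true Step 1 rate ratio of 1 and a common base rate B per 100 person-years, the observed ratio is (B + 1043.6 × p_CAB) / (B + 1043.6 × p_TDF), where 1043.6 = 100 × 365.25/35. The SAP gives neither B nor the shares, so all of these are assumptions.

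| Same-day share, CAB v TDF/FTC | B = 100 | B = 200 | B = 400 |
|---|---|---|---|
| 1% v 0.2% | 1.08 | 1.04 | 1.02 |
| 2% v 0.5% | 1.15 | 1.08 | 1.04 |
| 5% v 0.5% | 1.45 | 1.23 | 1.12 |
| 1% v 1% | 1.00 | 1.00 | 1.00 |

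**The case against.** The strongest reply is that little depends on this overlap. Sections 7.3.3 and 7.3.4 are separate analyses with different objectives, and the SAP never adds them together, so an event that appears in both does not inflate a total. The primary safety comparison covers Steps 1 and 2 together and does not use this boundary. Only grade 2 or higher events enter the formal comparison, both arms receive an injection, and injection site reactions are tabulated separately, so an injection-site term in a Step 1 table would be noticed.

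Most of this stands, and it limits the point to one supporting analysis. It does not make the Step 1 rule right. Being able to recognize an injection-site term in a table does not take it out of the modelled rate, and a systemic same-day reaction would carry no such label.

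Two stronger readings are tempting:

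- A reader might infer that the overlap creates a false difference between the arms. The documents do not show this. They give no same-day rates, and equal shares on equal base rates leave the ratio at 1.00.
- A reader might also count the date-imputation rules in Section 8.2 as part of the same fault, since "If start date is completely missing, start date is set to date of first dose" and a missing day in a later month goes to the 1st. Those rules can move an event from Step 2 into Step 1, but it is then counted once, so this is a different matter from the overlap. Barring imputed dates before the injection for events first reported at a Step 2 visit would do harm. Week 5 is itself a Step 2 visit, so run-in events first reported there would be pushed into the injection phase.

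A fair caution remains about the remedy. The SAP works with dates, and some same-day findings will have been present before the injection. Any tie rule will misplace a few events, so the rule should use whatever documentation exists.

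**Conclusion.** The point holds as a wrongly stated boundary. As written, an adverse event dated on the day of the first injection, including a reaction to the injection, is counted in the oral run-in comparison and again in Step 2. This conflicts with the Step 1 objective and with Appendix A, which assigns that day to Step 2.

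For one arm's Step 1 rate, the effect is up to about 10 per 100 person-years for each 1% of women with a grade 2 or higher event that day. It rests on a 35-day run-in and on shares that the SAP does not supply. The effect on the ratio between arms cannot be determined from the SAP and may be nil. The pooled primary safety result does not change. The correction should be made before the Step 1 tables are programmed, but the point does not threaten the trial's main safety conclusion.

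**What to change.** State one non-overlapping rule, in matching words, in Sections 7.3.3 and 7.3.4:

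- **Step 1** counts adverse events dated before the first injection, plus events dated on that day that are documented as present before the injection, such as findings from pre-injection assessments at the Week 5 visit.
- **Step 2** counts all other events dated on that day, every injection site reaction, and later events up to the OBSP censoring time. It excludes the same-day events assigned to Step 1.

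Leave Section 8.2 as it is.

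The cost is a sentence or two in each section, a changed inequality in the programs, and a flag for same-day events documented as present before the injection, set without knowledge of arm. The downside is small: a few same-day events of unknown timing that truly began in the run-in will fall in Step 2, where the longer follow-up means that they hardly move the rate.
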